10. SAFETY

10.1. Evaluations

Safety and tolerability will be evaluated by solicited local and systemic reactions (immediate complaints within 15 minutes post-vaccination and solicited reactions up to seven days post-vaccination), unsolicited AEs up to 21 days post-vaccination, and serious adverse events (SAEs) and new onset of chronic diseases (NOCDs), and AEs leading to withdrawal up to the end of the surveillance period. In addition, events will be monitored for a possible hypersensitivity component, from all reported events during the study (collected AEs, SAEs, NOCDs, and AEs leading to withdrawal).

Subjects will be monitored for both solicited local reactions (erythema, swelling, and pain at the injection site) and solicited systemic reactions (fever, headache, fatigue, muscle aches, joint aches, chills, a feeling of general discomfort, swelling in the axilla, and swelling in the neck) from the time of vaccination through Day 7. While the subjects remain in the clinic following vaccine administration, staff will monitor them for local and systemic reactions; after release from the clinic facility, from the evening of Day 0 to the evening of Day 7, subjects will measure and record their local and systemic reactions in their diary.

The intensity of the solicited local and systemic reactions will be graded as: mild (1), moderate (2), severe (3), or potentially life threatening (4) (please refer to Table 4). Their causal relationship with the study vaccine will be assessed by the Investigator (definitely not related, probably not related, probably related or definitely related).

Table 4 Severity Grades for Solicited Local and Systemic Reactions

Symptoms	Severity					
	None	Grade 1 (Mild)	Grade 2 (Moderate)	Grade 3 (Severe)	Grade 4 (Potentially life- threatening)	
Injection Site Reaction	ns (Local Rea	ections)				
Erythema (redness)	< 25 mm	25 - 50 mm	51 - 100 mm	> 100 mm	Necrosis or exfoliative dermatitis	
Swelling	< 25 mm	25 - 50 mm and does not interfere with activity	51 – 100 mm or interferes with activity	> 100 mm or prevents daily activity	Necrosis	
Pain	None	Does not interfere with activity	Repeated use of non-narcotic pain reliever for more than 24 hours or interferes with activity	Any use of narcotic pain reliever or prevents daily activity	Results in a visit to emergency room (ER) or hospitalization	
Solicited Systemic Re	actions					
Fever (°C or °F)	< 38.0 °C < 100.4 °F	38.0 - 38.4 °C 100.4 - 101.1 °F	38.5 - 38.9 °C 101.2 - 102.0 °F	39.0 - 40.0 °C 102.1 - 104.0 °F	> 40.0 °C > 104.0 °F	

Symptoms	Severity					
	None	Grade 1 (Mild)	Grade 2 (Moderate)	Grade 3 (Severe)	Grade 4 (Potentially life- threatening)	
Headache	None	No interference with activity	Repeated use of non-narcotic pain reliever for more than 24 hours or some interference with activity	Significant; any use of narcotic pain reliever or prevents daily activity	Results in a visit to emergency room (ER) or hospitalization	
Fatigue	None	No interference with activity	Some interference with activity	Significant; prevents daily activity	Results in a visit to emergency room (ER) or hospitalization	
Muscle aches	None	No interference with activity	Some interference with activity	Significant; prevents daily activity	Results in a visit to emergency room (ER) or hospitalization	
Joint aches, chills, feeling of general discomfort or uneasiness (malaise), swelling in the axilla, swelling in the neck	None	No interference with activity	Some interference with activity not requiring medical intervention	Prevents daily activity and requires medical intervention	Results in a visit to emergency room (ER) or hospitalization	

10.2. Adverse Events

All Adverse events (AEs) will be classified by Primary SOC and PT according to the Medical Dictionary for Regulatory Activities (MedDRA®) Version 21.0 or higher. An AE is considered treatment-emergent if it began on or after the date and time of Study Day 0 vaccination.

All spontaneous AEs occurring within 21 days after vaccination will be reported in the "Adverse Event" screen in the subject's eCRF, irrespective of intensity or whether or not they are considered to be vaccination-related. Thereafter, from Day 22 to the end of the surveillance period, SAEs, AEs leading to withdrawal, and NOCDs will be monitored and reported in the eCRF.

The intensity of AEs will be graded as: mild (1), moderate (2), severe (3) or potentially life threatening (4), according to the Food and Drug Administration (FDA) Guidance for Industry (FDA, 2007). Their causal relationship with the study vaccine will be assessed by the Investigator (definitely not related, probably not related, possibly related, probably related or definitely related); see Section 13.1.9 in protocol for a definition of these causal relationships.

10.3. Analysis of Secondary Endpoints

The secondary endpoints of safety that are mentioned in Section 4.2.1 will be analyzed as follows: All safety analyses will be based on the SAS.

Safety and tolerability endpoints (immediate complaints, solicited local and systemic reactions, and TEAEs, deaths, SAEs, AEs leading to subject withdrawal, and NOCDs) will be summarized by treatment and by age group using descriptive statistics.

The original terms used in the eCRFs by Investigators to identify AEs will be coded using the MedDRA® dictionary. All eCRF reported AEs with onset post-vaccination will be included in the safety analyses.

Special attention will be given to those subjects who die, who discontinue from the study due to an AE, who experience an SAE (e.g. summaries, listings, and narrative preparation may be provided, as appropriate), or who experience an allergic or allergic-like reaction (hypersensitivity cases).

Overall summaries of subjects with solicited reactions and Unsolicited Treatment Emergent Adverse Events (TEAE) will be prepared as follows:

- Any solicited local and systemic reactions occurring 15 minutes after vaccination (immediate complains)
- Solicited reactions including immediate complains
- Severe and potentially life-threatening solicited reactions
- Severe and potentially life-threatening related solicited reactions
- Solicited local reactions
- Solicited systemic reactions
- Unsolicited TEAEs (Day 0 to Day 21)
- Related unsolicited TEAEs
- Severe and potentially life-threatening unsolicited TEAEs
- Severe and potentially life-threatening related unsolicited TEAEs
- Serious TEAEs (Day 0 to Day 21)
- Serious TEAES (Day 0 to End of study)

The percentage of subjects with at least one immediate complaint (local or systemic reactions) and the percent of subjects with at least one immediate complaint of each of the individual local and systemic reactions will be summarized by treatment group and by age group.

In addition, the same summary will be tabulated by maximum severity grading and by causality for each treatment group overall and by age group.

The maximum event severity will be considered to be the greatest severity associated with each reaction according to the following order: mild < moderate < severe <potentially life-threatening. Causality will be presented as "Unrelated" (definitely not related and probably not related) and "Related" (possibly related, probably related and definitely related).

Similar summaries will be presented for solicited local and systemic reactions collected from Day 0 to Day 7 and unsolicited TEAEs collected up to Day 21. In addition, summaries of severe and potentially life-threatening solicited local and systemic reactions and unsolicited TEAEs will also be provided.

The analysis of unsolicited adverse events comprises the following categories:

- Occurrence of any unsolicited TEAE by system organ class (SOC) and PT from the administration of the vaccine dose up to day 21 (day 0 to day 21)
- Unsolicited TEAEs by SOC, PT and Maximum severity (Day 0 to 21)
- Unsolicited TEAEs by SOC, PT and relationship status (Day 0 to 21)
- Grade 3 and Grade 4 related unsolicited TEAEs by SOC and PT (Day 0 to Day 21)

AE summary tables will be presented for the below categories as well:

- AEs leading to death (Day 0 to End of study)
- Serious TEAEs (Day 0 to Day 21) by SOC and PT
- Serious TEAEs (Day 0 to End of study) by SOC and PT
- AEs leading to withdrawal (Day 0 to End of study)
- Occurrence of New Onset of a Chronic Disease (NOCD)s (Day 0 to Day 21) by SOC and PT
- Occurrence of NOCDs (Day 0 to End of study) by SOC and PT
- Occurrence of Hypersensitivity Cases (Day 0 to Day 21) by SOC and PT

Events that are considered to be a new onset of chronic disease (NOCD), as defined in the study protocol, will be collected until the end of surveillance. A summary of the occurrence of NOCDs, by SOC and PT, will be provided for Day 0 to Day 21 and from Day 0 to the end of surveillance.

Hypersensitivity cases will be identified using a standardized MedDRA® query (SMQ) for hypersensitivity. A summary of the occurrence of hypersensitivity events, by SOC and PT, will be provided for Day 0 to Day 21.

In summaries by SOC and PT, events will be sorted by internationally order (please refer to Appendix A).

Where the same reaction or same adverse event, based on preferred terminology, is reported multiple times for the same subject in a treatment period, the subject will only be counted once in the preferred terminology level in summary frequency tables.

Individual listings will be provided for the categories below:

- Solicited local and systemic reactions Day 0 to Day 7
- Unsolicited AEs (Day 0 to Day 21)
- Serious TEAEs (Day 0 to End of Surveillance)
- NOCD (Day 0 to End of Surveillance)
- Hypersensitivity Cases (Day 0 to Day 21)

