13.1.3 Adverse Events of Special Interest

In the five studies conducted to date, all reported events were monitored for a possible hypersensitivity component (events were searched using both narrow and broad standardized MedDRA® queries). Based on these data, there is no evidence of anaphylactic reactions associated with use of the Quadrivalent VLP Influenza Vaccine in humans: a small number of subjects had potential hypersensitivity reactions judged to be related to vaccine administration (no more than 0.3 % of subjects in any given VLP treatment group experienced one of these events) and the events were distributed fairly evenly among treatment groups, including the placebo and the active comparator groups. However, since severe reactions are considered to be an important potential risk (based on the theoretical risk that using plants for the production of

Medicago R&D Inc. Page 66 of 90

biotherapeutics may induce hypersensitivity) the sponsor will continue to require that appropriate medical treatment and supervision are available to manage any possible anaphylactic reactions.

To collect additional data on these events, Medicago will closely monitor and assess allergic or allergic-like reactions as AEs of special interest. Thus, to collect specific data under this protocol, the Investigator should, whenever possible, take a picture of any occurrence of allergic or allergic-like reactions and send the anonymized images to Medicago as described in the study-specific documentation.

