13.1.4 New Onset of Chronic Disease

In the context of this study, all NOCDs that may plausibly have an allergic, autoimmune or inflammatory component are to be reported. Plausibility should be interpreted broadly however; the only clear exceptions are degenerative conditions such as osteoarthritis, age-related physiologic changes (e.g. benign prostatic hypertrophy) and life-style diseases (e.g. alcohol-associated cirrhosis, bronchitis in a smoker, etc.). In this context, most cancers, cardiac conditions, and kidney diseases should be reported.

NOCDs will be collected from vaccination on Day 0 to the end of the surveillance period and reported as an AE or SAE, as applicable.

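### The hypersensitivity query output stops at Day 21, although hypersensitivity is to be monitored in all events reported during the study

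*SAP*

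**What the plan says.** On scope, SAP 10.1 states that "events will be monitored for a possible hypersensitivity component, from all reported events during the study". The parenthesis that follows names adverse events, SAEs, NOCDs and adverse events leading to withdrawal. Protocol 10.3.1 has the same sentence.

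On collection, all adverse events are recorded to Day 21. After that, SAP 10.2 narrows the scope: "from Day 22 to the end of the surveillance period, SAEs, AEs leading to withdrawal, and NOCDs will be monitored".

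On output, SAP 10.3 identifies cases with a standardised MedDRA query (SMQ) for hypersensitivity and gives the Day 21 limit three times:

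- in the list of summary tables: "Occurrence of Hypersensitivity Cases (Day 0 to Day 21) by SOC and PT";
- in the explanatory text: "A summary of the occurrence of hypersensitivity events, by SOC and PT, will be provided for Day 0 to Day 21";
- in the individual listings: "Hypersensitivity Cases (Day 0 to Day 21").

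On importance, protocol 13.1.3 says that "Medicago will closely monitor and assess allergic or allergic-like reactions as AEs of special interest", and calls severe reactions an important potential risk because the product is made in plants. Protocol 13.1.4 adds that "all NOCDs that may plausibly have an allergic, autoimmune or inflammatory component are to be reported", to the end of surveillance.

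**The concern.** The stated scope of monitoring and the planned output do not match. Three of the four event types named in SAP 10.1 are collected to the end of surveillance, yet the query that would pick out hypersensitivity among them is tabulated and listed only to Day 21. The limit is given three times in consistent form, so a programmer following SAP 10.3 would produce no later hypersensitivity output.

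At stake is how well the trial describes a risk that its own protocol singles out. About 6060 subjects are planned per arm, against 687 recipients of this vaccine aged 65 and older in the completed studies (protocol 1.3). That makes this a large randomised comparison with a licensed vaccine in the age group. A reader wanting late allergic events by arm would have to assemble them by eye from several general tables. If the query were extended only after unblinding, it would be a post hoc search.

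**Working it through.** The plan gives no figure to reproduce here. The main check sets the collection window beside the output windows in SAP 10.2 and 10.3.

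| Event type | Collected to | Summary tables in SAP 10.3 | Named listing in SAP 10.3 |
|---|---|---|---|
| All unsolicited adverse events | Day 21 | Day 0 to 21 | Day 0 to 21 |
| Serious events | End of surveillance | Day 0 to 21, and Day 0 to end of study | To end of surveillance |
| NOCDs | End of surveillance | Day 0 to 21, and Day 0 to end of study | To end of surveillance |
| Leading to withdrawal | End of surveillance | Day 0 to end of study | None named |
| Leading to death | End of surveillance, as SAEs | Day 0 to end of study | None named |
| Hypersensitivity (query) | Depends on the underlying event type | Day 0 to 21 only | Day 0 to 21 only |

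1. In the SAP 10.3 list of additional adverse event summaries (the last five rows), hypersensitivity is the only category without an end-of-study version.

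2. Take an SAE, NOCD or withdrawal event with onset after Day 21 and a term inside the query. It is recorded under SAP 10.2, falls within the monitoring scope of SAP 10.1, and reaches the relevant general end-of-study table. It enters neither the hypersensitivity table nor the hypersensitivity listing.

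3. The general tables cannot simply be added to recover the count. Protocol 13.1.4 has NOCDs reported as adverse events or SAEs as applicable, so one event can be both serious and an NOCD and can also lead to withdrawal. The same subject could then appear in three tables.

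4. SAP section 12 lists four changes from the protocol. None mentions a Day 21 limit on hypersensitivity.

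The only arithmetic is the share of follow-up that Day 21 covers. Inputs: eight to ten months of participation (SAP 3.4, protocol 4.1) and an assumed 30.4 days per month.

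- Eight months: 8 × 30.4 = 243 days; 21 / 243 = 8.6%.
- Ten months: 10 × 30.4 = 304 days; 21 / 304 = 6.9%.

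About 91% to 93% of planned follow-up therefore lies outside the hypersensitivity table and listing.

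**The case against.** The best defence is that Day 21 is the natural cut. It is the last day on which every adverse event is collected, so Day 0 to 21 is the only window with uniform ascertainment. A count to the end of surveillance would join all events before Day 21 to a selected subset after it, and would still miss late non-serious allergic events that are neither NOCDs nor a cause of withdrawal. The documents do not give this reason, but it follows from their collection rules. It stands as a reason to keep the Day 0 to 21 table and to label any longer one carefully. It does not explain why no longer one exists, since serious events and NOCDs get both windows.

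It can also be said that SAP 10.1 promises monitoring and not a whole-study table, and that hypersensitivity is not a named safety endpoint in SAP 4.2.1 or protocol 10.3.2. Both are true: no endpoint analysis is cut short. The mismatch is between the stated scope of monitoring and the only output planned to show its result.

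A reader might infer that late allergic events go unreported or lose their special-interest status. The documents do not support this. Such events remain in the end-of-study SAE, NOCD and withdrawal tables, and SAP 6.1 puts all subject data in listings. Protocol 13.1.3 sets no day limit on special-interest status. SAP 10.3 and protocol 12.5.1 also promise special attention to allergic reactions without one. Nor are NOCDs collected only for allergy: protocol 13.1.4 also names autoimmune and inflammatory components and is to be read broadly.

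**Conclusion.** The point holds as a gap in safety presentation. As SAP 10.3 is written, hypersensitivity-coded SAEs, NOCDs and withdrawal events after Day 21 are reported, but are not identified or counted by arm as hypersensitivity cases. The SAP neither explains this nor reconciles it with SAP 10.1.

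The size in cases is unknown. The documents give no expected number or time distribution of hypersensitivity events. The 7% to 9% is a share of time, resting on the stated eight to ten months and 30.4 days per month. It would be tempting to read it as meaning that over 90% of cases are missed. Nothing in the plan supports that, and late cases may be few or none.

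Data collection, sample size, power and the primary analysis are unaffected. This is a worthwhile improvement and not a threat to the trial's conclusions.

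**What to change.** In SAP 10.3, keep the Day 0 to 21 hypersensitivity table and listing as the window with uniform adverse event collection. Add a separate SMQ hypersensitivity table by arm, and a listing, from Day 0 to the end of surveillance, as is already planned for serious events and NOCDs. Footnote both additions to say that after Day 21 only SAEs, NOCDs and adverse events leading to withdrawal are collected, so late non-serious allergic events are incompletely captured. Specify this before unblinding.

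If the sponsor prefers the single window, SAP 10.3 should state and justify the Day 21 limit and SAP 10.1 should be reconciled with it.

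The cost is one more table and one more listing, with no new data. The downside is that the longer table mixes two levels of ascertainment, which the footnote must make plain.

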10.4. Analysis of Exploratory Endpoints

The exploratory safety endpoints defined in Section 4.2.2 will be analyzed as follows:

The occurrences of medical visits, hospitalizations, and workdays missed (if applicable) will be summarized by treatment using descriptive statistics. These analyses will be done separately and not be included in the CSR.

10.5. Vital Signs

Vital signs measurements (resting BP, HR, and OT) will be performed as part of screening procedures (during eligibility assessment on Day 0) and after the 15-minute post-vaccination surveillance period.

Vital signs data (actual values and Change from baseline) will be summarized by treatment group and assessment timepoint using standard summary statistics.

An individual listing will be provided for vital signs measurements by subject and age stratum.

10.6. Electrocardiograms

Electrocardiograms are not planned for this study.

10.7. Physical Examination

A history- or symptom-directed physical examination will be performed by the Investigator as part of screening procedures (during the eligibility assessment on Day 0).

An individual listing will be provided for Physical Examination results by subject and age stratum.

10.8. Other Safety

No other safety assessments are planned for this study.

Statistical Analysis Plan Sponsor: Medicago; Protocol No.: CP-PRO-QVLP-014

INTERIM ANALYSES 11.

No interim analysis is scheduled.

12. CHANGES FROM ANALYSIS PLANNED IN PROTOCOL

- 1). According to the scientific advices of European Medicines Agency (EMA), a new secondary efficacy endpoint is added:
 - Occurrences of laboratory-confirmed influenza illnesses (according to protocol defined ILI; ≥ 14 days post-vaccination) caused by any influenza viral types/subtypes (matched, mismatched, and un-typed) according to prior exposure to influenza vaccines.

The occurrence and vaccine efficacy (95% CI) for subjects with and without influenza vaccination history will be summarized.

- 2). A new exploratory efficacy endpoint is added:
 - To evaluate whether or not vaccine efficacy (VE) is maintained (no waning) through time after vaccination for the primary efficacy endpoint, that is, protocol-defined ILI caused by any influenza viral type/subtype.

The relevant analysis is described in Section 8.4.

3). Heterologous strains for the exploratory CMI data will not be analyzed due to the reason below:

As it was already demonstrated in previous clinical trials that the Quadrivalent VLP Influenza Vaccine elicited cross-reactive CD4 T cell response, it was decided to wait so see if the 2018-2019 season would be a match or a mismatch season. In case of a mismatch season, Medicago will therefore has the possibility to test the CMI response generated by the Quadrivalent VLP Influenza Vaccine against the strain(s) that were actually circulating during the season.

4). There is a discrepancy between the protocol and the SAP regarding the seroconversion calculations for MN titers. The definition used in the SAP (cut-off at 7.1) is the one prevailing over the protocol definition (in which it is said that the same approach as for HI titers will be used).

14. PROGRAMMING CONSIDERATIONS

14.1. General Considerations

- A separate SAS[®] program will be created for each output.
- Each output will be stored in a separate file.
- Output files will be delivered in Word format.
- Numbering of TLFs will follow International Conference of Harmonization (ICH) E3 guidance.

14.2. Table, Listing and Figure Format

14.2.1. General

- All TLFs will be produced in landscape format, unless otherwise specified.
- All TLFs will be produced using the Times New Roman font, size 10. A smaller font size can be used if the width of the table or listing would not fit well across a single page.
- The data displays for all TLFs will have a 1.5-inch binding margin on top of a landscape oriented page and a minimum 1-inch margin on the other 3 sides.
- Headers and footers for figures will be in the Times New Roman font, size 10. For headers, a smaller font size can be used if necessary.
- Legends will be used for all figures with more than 1 variable, group, or item displayed.
- TLFs will be in black and white (no color), unless otherwise specified
- Specialized text styles, such as bolding, italics, borders, shading, and superscripted and subscripted text, will not be used in the TLFs, unless otherwise specified. On some occasions, superscripts 1, 2, or 3 may be used (see below).
- Only standard keyboard characters will be used in the TLFs. Special characters, such as non-printable control characters, printer-specific, or font-specific characters, will not be used. Hexadecimal-derived characters will be used, where possible, if they are appropriate to help display math symbols (e.g., μ). Certain subscripts and superscripts (e.g., cm²) will be employed on a case-by-case basis.
- Mixed case will be used for all titles, footnotes, column headers, and programmer-supplied formats, as appropriate.

